## ATTACHMENTS

### 1. PERIOD ALLOCATION OF ADVERSE EVENTS

Solicited events will always be allocated to the Post-dose 1 or Post-dose 2 period, as appropriate.

Unsolicited AEs will be allocated to the different periods per the following rules:

#### ***Step 1: Allocation of unsolicited events to the periods/phases:***

The AEs present in the database are allocated to periods/phases based on their start date/time. If the start date/time of an event falls between (or on) the start and stop date/time of a period/phase, the AE is attributed to that period/phase (ie, AEs following vaccination).

Incomplete dates (ie, time and/or day and/or month and/or year missing):

- 1) In case of partial start or stop dates, the events are allocated to the periods/phases using the available partial information on start and end date; no imputation will be done. If, for instance, for the AE start date only month and year are available, these data are compared to the month and year information of the periods/phases. This rule may lead to multiplication of the event because of its assignment to multiple periods/phases (see below example).
- 2) In case of a completely missing start date, the event will be allocated to the appropriate period/phase (eg, Post-dose 1 or Post-dose 2) and consequently the Regimen period; except if the end date of the AE falls before the start of the Post-dose 1 or Post-dose 2 period.
- 3) In case of a completely missing end date (only for the calculation of duration):
  - In case the AE is flagged as ongoing the date is imputed by the cut-off date of the analysis for subjects still ongoing in the study, and by the end date of the last period/phase for subjects who discontinued or completed the trial.
  - In case the AE is not flagged as ongoing, the end date is considered as unknown, and the date will remain missing.

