**Table 2: Analysis Periods**

Phase	Period	Interval	
		From	To
Screening		00:00 on the date of signing the informed consent form	One minute prior to Dose 1 administration on Day 1
Regimen*	Post-dose 1	Date and time of Dose 1 administration	Minimum of: a) 23:59 on the date of last contact (for early study discontinuations) b) 23:59 on the date of relative Day 29 Post-dose 1 c) one minute prior to Dose 2 administration
Post-dose 1 FU		One minute after the end of the Post-dose 1 period	Minimum of: a) 23:59 on the date of last contact (for early study discontinuation or completion) b) one minute prior to Dose 2 administration
Regimen*	Post-dose 2	Date and time of Dose 2 administration	Minimum of: a) 23:59 on the date of last contact (for early study discontinuation or completion) b) 23:59 on the date of relative Day 29 Post-dose 2  Note: subjects who do not receive Dose 2 will not have a Post-dose 2 period.
Post-dose 2 FU		One minute after the end of the Post-dose 2 period	23:59 on the date of last contact (for early study discontinuation or completion)

**Note 1:** \* Regimen period includes both the Post-dose 1 and Post-dose 2 periods.

**Note 2:** FU = follow-up.

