### 7.1.3. Analysis Methods

In general, the AEs following vaccination will be summarized (ie, tables of descriptive statistics) by vaccination schedule and presented per period/phase. The presentation will be according to the cohorts as shown in

[Table 4](#). Similar summary tables will also be provided pooled by vaccine (dose).

Furthermore, unsolicited AEs will be summarized (showing number and percentage) by System Organ Class (SOC) and Preferred Term (PT). Solicited AEs (recorded by day) will be converted into the analysis format of unsolicited AEs (recorded by event), as detailed in Attachment 2. These solicited AEs will be summarized by class (local, systemic) and Preferred Term. For solicited as well as unsolicited AEs, tables focusing on severity will be created. Focus will also be on the relationship (to the study vaccine) of the solicited systemic and unsolicited AEs.

The SAEs, AEs with fatal outcome, AEs leading to permanent discontinuation from boost vaccine administration, Grade 3 AEs and IREs will also be listed. A table summarizing all those parameters will further be created and presented per analysis period and vaccination schedule. Summary tabulations by SOC and PT for each of the category of events (ie, SAEs, AEs with fatal outcome, AEs leading to permanent discontinuation from boost vaccination, Grade 3 AEs and immediate reportable events) will also be generated on the entire reporting period and presented by vaccination schedule. Subject narratives will be generated for these events, except Grade 3 AEs. For Grade 3 AEs, the narratives will only be generated for those AEs that are considered related to study vaccination.

For the most frequent (at least 10% of subjects in any vaccination schedule) solicited local and systemic AEs, the duration and time to first onset of the events will also be summarized. If a subject experiences more than 1 occurrence of a solicited event, the maximum duration of the events will be used. The time to first onset is defined as:

$$[\textit{date of first onset} - \textit{reference date} + 1]$$

The reference date is the start date of each vaccination period (ie, Post-dose 1 or Post-dose 2). Duration and time to onset of AEs will be expressed in days.

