#### **Remarks:**

- In addition to the date information, time information is considered to allocate AEs to periods, if available.

- The imputation of missing end dates of ongoing AEs will only be used to derive the duration of the event (ie, to give an indication of the minimum duration). The imputed end dates will not be shown in the data listings.

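### An unsolicited AE dated on the boost day with no start time is counted in Post-dose 1 as well as Post-dose 2 when the boost falls on or before Day 29, which by schedule happens only in Group 1

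*SAP*

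**What the plan says.** SAP Attachment 1, Step 1 allocates unsolicited AEs by start date and time. It defines its special case as "Incomplete dates (ie, time and/or day and/or month and/or year missing", so a missing time alone makes a date incomplete. For such records, "the events are allocated to the periods/phases using the available partial information on start and end date; no imputation will be done". It then accepts the consequence: "This rule may lead to multiplication of the event because of its assignment to multiple periods/phases". The Remarks that follow add: "In addition to the date information, time information is considered to allocate AEs to periods, if available". No rule is given for a complete date whose time is absent.

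SAP Table 2 ends Post-dose 1 at the earliest of last contact, "23:59 on the date of relative Day 29 Post-dose 1", and "c) one minute prior to Dose 2 administration". Post-dose 1 FU starts a minute after Post-dose 1 ends and also runs to "one minute prior to Dose 2 administration". Post-dose 2 starts at Dose 2.

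SAP Section 7.1 limits the AE analysis to Post-dose 1, Post-dose 2 and the Regimen phase; the FU phases are not among them. Section 7.1.3 tabulates AEs by schedule and period, and adds: "Similar summary tables will also be provided pooled by vaccine (dose").

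Protocol Section 6.1 places the boost on Day 29, 57 or 85 for Groups 1, 2 and 3. Protocol Table 3 allows one day either side.

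**The concern.** The period before the boost is an analysed vaccine period for some subjects and an unanalysed follow-up phase for others. Which one applies depends on whether the boost came by Day 29. A rule that copies an event into every period touching its date therefore does different things to the same event in different schedules.

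Adverse events are a primary endpoint (protocol Section 9.2.1), and the prime is identical in all three groups. A reader comparing Post-dose 1 columns across schedules will expect them to differ only by chance and by observation time. Events dated on the day of the MVA-BN-Filo boost can enter that column in Group 1 but not in Groups 2 and 3. Group 1 is also split internally: a Day 29 boost duplicates the event into Post-dose 1, while an in-window Day 30 boost does not. The per-period table of SAEs, Grade 3 AEs and IREs in Section 7.1.3 is exposed in the same way.

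**Working it through.** **1. Reproduce the SAP's own periods.** The example under Attachment 1, Step 2 has Post-dose 1 from 28JUN2016 to 26JUL2016 and Post-dose 1 FU from 27JUL2016. With the prime as Day 1, Day 29 is 28 June + 28 days = 26 July, and FU opens the next day. Table 2, as coded for this check, gives the same dates.

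**2. Apply Step 1 to an AE dated on the boost day.** The check used a prime at 10:00 on 28JUN2016 and a boost at 10:00. The AE was entered once with its date only and once with a time of 14:00.

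| Boost day | Date only | Time 14:00 recorded |
|---|---|---|
| 28, 29 (Group 1) | Post-dose 1 + Post-dose 2 | Post-dose 2 |
| 30 (Group 1, in window); 31, 40, 41 | Post-dose 1 FU + Post-dose 2 | Post-dose 2 |
| 56-58 (Group 2) | Post-dose 1 FU + Post-dose 2 | Post-dose 2 |
| 84-86 (Group 3) | Post-dose 1 FU + Post-dose 2 | Post-dose 2 |
| 120 (late boost) | Post-dose 1 FU + Post-dose 2 | Post-dose 2 |

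On Day 28 or 29, Post-dose 1 is still open that morning. From Day 30 it has already closed at 23:59 on Day 29.

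**3. Look for anything that removes the duplicate.** The Remarks use time only when it exists. Step 2, rule 4 keeps events in two successive active periods as separate AEs. Neither removes the copy.

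**4. Identify the outputs affected.**
- Affected: Post-dose 1 tables for Group 1, and the by-dose Ad26.ZEBOV table.
- Not affected: solicited AEs, which follow their own allocation rule; Regimen-phase subject counts, where a subject counts once; and the SOC/PT tables over the entire reporting period.
- On the prime date the same overlap exists in all groups, but the extra copy goes to Screening.

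**5. Illustrate the size.** The documents give neither the frequency of missing AE times nor the rate of boost-day unsolicited AEs, so both inputs are assumptions. Let p be the share of Group 1 subjects who were boosted by Day 29 and have a date-only unsolicited AE on that date. Let q be the share with another Post-dose 1 unsolicited AE, taken as independent. The rise in Group 1 Post-dose 1 incidence is p(1 - q). For scale, take the planned 164 active Group 1 subjects in Cohorts II and III, out of 492 over three groups (164/492 = 1/3).

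| p | Rise, q = 50% to 30% | Extra subjects of 164 | Rise in by-dose column (one third) |
|---|---|---|---|
| 2% | 1.0-1.4 points | 1.6-2.3 | 0.33-0.47 points |
| 5% | 2.5-3.5 points | 4.1-5.7 | 0.83-1.17 points |
| 10% | 5-7 points | 8.2-11.5 | 1.67-2.33 points |

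The corresponding rise in Groups 2 and 3 is 0. For a single preferred term q is small, so nearly all of p shows: with 1% true Post-dose 1 incidence and p = 2%, the table shows 1% + 2% × 0.99 = 2.98%, about 3%. With every start time recorded, p = 0 and the rise is 0.

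**The case against.** The SAP discloses the multiplication. Counting an event in every compatible period without imputing is a recognisable conservative convention in safety work. That stands as a defence of the general rule, especially for dates missing a day or month. It does not explain why the extra copy should reach an analysed period in one schedule only, and the SAP does not mention that it does.

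The size may be very small. Common reactions on the boost day are solicited and bypass this rule. Staff observe subjects for about an hour after vaccination, so many onset times may be recorded. SAP Section 1.4 says many subjects had a late boost or none, which takes them out of the overlap. All of this stands, and the larger values of p above have no support in the documents.

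The most substantive objection concerns direction. Before the boost injection, subjects have laboratory tests, ECG, vital signs and a symptom-directed examination (protocol Section 9.1.3). A clinically significant finding there may carry the boost date with no time. In Group 1 its correct period is Post-dose 1, and the present rule keeps it there; the misplaced copy is then the one in Post-dose 2. A tie-break that always chose Post-dose 2 would lose the correct count, so the fix needs an exception.

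Three stronger readings are tempting but not supported. A reader might infer that boost-day events are moved to the prime; they are added there and remain in Post-dose 2. A reader might infer that Group 1 post-prime rates are necessarily overstated; that holds only for date-only events that began after the injection. A reader might infer an inflated active-placebo difference; placebo events are duplicated too, so this needs a further assumption that date-only boost-day events are more frequent after MVA-BN-Filo than after placebo.

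**Conclusion.** The point holds as a narrow asymmetry in the allocation rule. Read literally, SAP Table 2 and Attachment 1, Step 1 put a date-only boost-day unsolicited AE into Post-dose 1 in addition to Post-dose 2 for Group 1 subjects boosted by Day 29. For everyone boosted later, the extra copy goes to a phase that the AE summaries leave out. Compared with a single allocation to Post-dose 2, the rule can only add to the Group 1 Post-dose 1 column and, at roughly one third of the size on planned numbers, to the Ad26.ZEBOV by-dose column.

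How much it adds is unknown. It depends on how many Group 1 subjects were boosted by Day 29, how many had an unsolicited onset that day, and how often the time is missing. No formal testing is planned, so the consequence is a distorted descriptive comparison between schedules and not a wrong test result. The case for changing it is that the asymmetry is arbitrary, affects a primary-endpoint table and is cheap to remove.

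**What to change.** Add to SAP Attachment 1, Step 1: *An unsolicited AE with a complete start date equal to a vaccination date and a missing start time is allocated only to the period that begins with that vaccination, unless the record shows that onset preceded the injection (eg, a finding at a pre-vaccination assessment that day), in which case it is allocated only to the preceding period/phase.* Keep multiple allocation for dates missing the day, month or year.

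Without a record of earlier onset, this puts the date-only event in Post-dose 2 alone for every boost day tested (28 to 120), which matches the result when a post-boost time is recorded. The difference between schedules disappears.

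The cost is one sentence, one programming condition and a check of boost-day records for evidence of onset before the injection. There is a small downside: a date-only AE that did begin before the injection, with nothing recorded to show it, would be counted only in Post-dose 2 and would lose the Post-dose 1 count that it has now in Group 1.

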#### **Examples:**

Screening Phase: start date: 14JUN2016 - stop date: 28JUN2016  
 Post-dose 1 period: start date: 28JUN2016 - stop date: 19JUL2016

1) Adverse event: start date: JUN2016- stop date: 15JUL2016

As the start date only has information about month and year, only this information will be used from the periods/phases (ie, assuming any day of Jun is possible) and therefore the AE will be assigned to the Screening Phase as well as to the Post-dose 1 period.

2) Adverse event: start date: JUL2016- stop date 14JUL2016

As the AE starts after the Screening Phase and after the start of the Post-dose 1 period, it is only assigned to the Post-dose 1 period.

#### **Remarks:**

- In addition to the date information, time information is considered to allocate AEs to periods, if available.

- The imputation of missing end dates of ongoing AEs will only be used to derive the duration of the event (ie, to give an indication of the minimum duration). The imputed end dates will not be shown in the data listings.

### **Step 2: Combination of events:**

Overlapping/consecutive events are defined as events of the same subject with the same preferred term which have at least 1 day overlap or for which the start date of an event is 1 day after the end date of the preceding event. Overlapping/consecutive events may be combined into one AE or not, according to the following rules:

- 1) If overlapping/consecutive events start in a non-active phase (Screening or any of Post-dose FU phases) followed by an AE in an active (Post-dose 1 or Post-dose 2) period, they are allocated to their respective periods/phases and are considered as separate events.
- 2) In case overlapping/consecutive events start within a single period/phase, they are considered as one and the same AE. The individual events which contribute to this AE are retained as individual records in the Analysis Data Model (ADaM) database but are assigned the same onset, period/phase, and total duration.
- 3) In case overlapping/consecutive events start in an active period followed by a non-active phase, they are allocated only to the active period and are considered as one and the same AE. The individual events which contribute to this AE are retained as individual records in the ADaM database but are assigned the same onset, period, and total duration.
- 4) In case an active period is followed by another active period, and the overlapping/consecutive events start in both periods, they are allocated to their respective period and are considered as separate AEs. The same rule applies for 2 non-active phases.
  - Remarks:
    1. Time is not considered when determining overlap of events.
    2. Events can only be combined into one and the same AE if their start and stop dates are known.
    3. In case the completely missing end date is imputed (for period allocation), this date is also considered as a complete date.

#### Examples:

Screening phase: start date: 14JUN2016 - stop date: 28JUN2016

Post-dose 1 period: start date: 28JUN2016 - stop date: 26JUL2016

Post-dose 1 FU phase: start date: 27JUL2016 - stop date: 15AUG2016

#### Example for the above Scenario 1

AE1: start date: 20JUN2016- stop date: 10JUL2016

AE2: start date: 08JUL2016- stop date: 18JUL2016

AE1 will be attributed to the Screening Phase and AE2 to the Post-dose 1 period.

#### Example for the above Scenario 3

AE1: start date: 18JUL2016- stop date: 28JUL2016

AE2: start date: 28JUL2016- stop date: 08AUG2016

As AE1 starts in the active period (Post-dose 1) and overlaps with AE2 which starts in a non-active phase (Post-dose 1 FU), this AE is considered as a single AE in the AE analysis starting on 18JUL2016 and ending on 08AUG2016 and is attributed to the Post-dose 1 period.

## 2. TRANSFORMING ON-SITE ASSESSMENTS AND DIARIES OF SOLICITED ADVERSE EVENTS INTO AN ANALYSIS FORMAT

When creating the analysis dataset for solicited AEs, solicited AEs (recorded by day) need to be converted into the format of unsolicited AEs (recorded by event). All diary data will be considered, as well as any post-dose on-site assessment (scheduled as well as unscheduled) within (including the day of vaccination) 8 days after vaccination. For solicited local AEs for which a diameter is measured, the maximum of diameter derived grade and investigator severity (if available) will be used. The start date of the AE will be considered as the date of first occurrence of the solicited AE (both local and systemic). If on subsequent day(s), the same grade is reported, the last reported date is used as the end date of the AE. A new record is created in case the grade of the event changes. If there is a time gap of at least one day between two (or more) occurrences of the same type of the solicited AE, then the second (and/or next) occurrence will be considered as a new AE. In case no data is reported for a day, this is analyzed as no event reported. If the on-site assessment differs in grade or relatedness (if collected) with the corresponding diary data, only the highest grade and the relatedness that most implicates the vaccine per AE will be kept in the analysis database and used in the tables and listings. The following example shows how the solicited AE should be converted into a format of unsolicited AEs:

### Data from the Subject Diary

Subject: PPD

Solicited systemic AE: Headache

Solicited AE	On-site Assessment	Diary Data							
	Day 1	Day 1	Day 2	Day 3	Day 4	Day 5	Day 6	Day 7	Day 8
	PPD	PPD	PPD	PPD	PPD	PPD	PPD	PPD	PPD
Grade	2	1	1	0	3	3	1	0	0
Relatedness	Doubtful	Probable							

The data should be converted and stored in the AE dataset as follows:

Subject No.	AE	Start Date (Char)	Stop Date (Char)	Severity	Relatedness	AEID
PPD	Headache	PPD	PPD	2	Probable	1
PPD	Headache	PPD	PPD	3	Probable	1
PPD	Headache	PPD	PPD	1	Probable	1

**If a solicited AE ends after Day 8:**

The stop date of the event is the “Date of last day of symptom” as recorded in the eCRF and the “maximum severity” after Day 8 as recorded in the CRF. A separate record is created for this, in case this severity deviates from the previous record.

**Note:** To complete the start and end-date based on diary data, the date will be calculated based on the day the AE is reported relative to vaccination and not on the reported date. For example, if the vaccination is on 01-JAN-2016, and the AE starts on Day 3, the start date will be set to the 03-JAN-2016, independent of the reported actual date.

For the calculation of duration, the first and last day is used, irrespective of whether interruptions occurred in between by missing reporting days or Grade 0 events. In the above example, the 4 records contribute to the same AE, therefore AEID is set to the same value and the duration of the AE is set to 6 for all records.

It is important to note that the occurrence of solicited injection site reaction and/or solicited systemic adverse events considered to be related to the study vaccine and persisting for at least 3 days will result in a study pause. However, the above rule for calculating duration of AEs may incorrectly indicate that the pausing rule is met. Therefore, a listing of subjects with Grade 3 (severe) AEs will be generated with an indication that interruption between AE start and AE end are not considered in the calculation of the duration of the AEs.

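### SAP Attachment 2 gives two conflicting definitions of a solicited AE interrupted by a symptom-free or unreported day, so its own headache example is one AE of 6 days or two AEs of 2 and 3 days

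*SAP*

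**What the plan says.** SAP Attachment 2 converts daily solicited symptom reports into event records. Its opening text has a change of grade open a new record. It treats a gap differently: where at least one day separates two occurrences of the same symptom, "then the second (and/or next) occurrence will be considered as a new AE". On unreported days it says "In case no data is reported for a day, this is analyzed as no event reported".

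A headache diary is then offered to show how the conversion works ("The data should be converted and stored in the AE dataset as follows"). Day 3 is Grade 0 and lies between symptomatic days, yet every row of the stored dataset as extracted carries AEID 1.

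The notes that close the attachment give the duration rule: "For the calculation of duration, the first and last day is used, irrespective of whether interruptions occurred in between by missing reporting days". Days at Grade 0 are bridged in the same way. For the example they say "AEID is set to the same value and the duration of the AE is set to 6 for all records". They also concede that "the above rule for calculating duration of AEs may incorrectly indicate that the pausing rule is met". The response is a listing of Grade 3 AEs stating that "interruption between AE start and AE end are not considered in the calculation of the duration of the AEs".

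SAP 7.1.3 summarises durations for solicited AEs seen in at least 10% of subjects in any schedule, with this provision: "If a subject experiences more than 1 occurrence of a solicited event, the maximum duration of the events will be used".

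**The concern.** The gap sentence and the closing notes assign AE identity differently for the same data. The example is presented as an illustration of the opening text but does not follow its gap sentence. Two programmers working faithfully from this attachment could produce different AEIDs and different durations.

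At stake are a descriptive summary under the primary safety objective and a listing. A first-to-last span with no label can be taken for a continuous episode. In the Grade 3 listing, a severe record would show a duration made up partly of days at lower grades or with no symptom.

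**Working it through.** **Inputs.** From the example in SAP Attachment 2: on-site grade on Day 1 is 2; diary grades for Days 1 to 8 are 1, 1, 0, 3, 3, 1, 0, 0. The attachment keeps the higher grade when on-site and diary differ, so Day 1 becomes 2.

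| Day | 1 | 2 | 3 | 4 | 5 | 6 | 7 | 8 |
|---|---|---|---|---|---|---|---|---|
| Grade used | 2 | 1 | 0 | 3 | 3 | 1 | 0 | 0 |

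**Reproducing the SAP's own figures.**
- Records by the grade-change rule: Day 1 (Grade 2), Day 2 (Grade 1), Days 4–5 (Grade 3), Day 6 (Grade 1), which is 4 records, as the notes say. The table as extracted shows three rows. That may be a PDF loss, and nothing here rests on it.
- Duration = last symptomatic day − first symptomatic day + 1 = 6 − 1 + 1 = 6 days, as stated.

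**Applying the gap sentence literally.** Day 3 separates two episodes:
- Days 1–2: 2 − 1 + 1 = 2 days.
- Days 4–6: 6 − 4 + 1 = 3 days.
- Maximum under SAP 7.1.3: 3 days.

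**Comparison.** Symptomatic days are 1, 2, 4, 5 and 6, a total of 5. The 6-day span is 6/3 = 2.0 times the longest episode and 6/5 = 1.2 times the symptomatic days. Time to first onset is 1 day under either rule, because the first occurrence is the same.

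**The Grade 3 record.** It covers Days 4–5, so 2 consecutive days. Under the closing notes it carries 6. Under the gap sentence it would still carry 3 if the AE's duration is copied to all its records. The solicited systemic pausing criterion in protocol 9.2.3 involves a Grade 3 reaction persisting for 3 or more days. Both 6 and 3 reach that length; the 2 Grade 3 days do not. The criterion also needs three or more subjects, so one record cannot meet it alone.

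**Hypothetical diaries, to show the range.**

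| Symptomatic days | First-to-last span | Longest episode |
|---|---|---|
| 1 and 8 | 8 | 1 |
| 1, 3, 5 and 7 | 7 | 1 |

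These show what the rules can do, not what the trial data contain.

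**The case against.** The best defence is that duration itself is not in doubt. The closing notes contain the only explicit duration rule for solicited AEs, with a worked answer; the SAP never prints 3 days. That stands: 6 is the likelier programmed result, and the 3 comes from joining the gap sentence to SAP 7.1.3.

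A second defence reads AE in the gap sentence as a dataset line. The opening text does end an AE when a run of equal grades ends, which is how a line behaves. The reading is possible but strained: the same paragraph has a separate sentence on new records, and the notes settle AE identity as well as duration.

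Third, the maximum rule in SAP 7.1.3 might seem to show that gapped episodes were meant to be separate. It does not, because the Regimen phase spans both doses, and a headache after each dose is already more than one occurrence. The rule fits either definition.

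Fourth, the note required in the Grade 3 listing warns the reader. It does, but the listed number stays as it was, and the duration summary gets no such note.

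A reader might also infer that reported reactogenicity rates are affected. The documents do not support that: tabulations count subjects with at least one occurrence, and no planned table counts solicited events. Nor do they support the inference that vaccination was paused because of this rule. Protocol 9.2.3 places pausing with the investigators and the medical monitor during the study, not with these outputs.

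**Conclusion.** The contradiction on AE identity is real and sits in the current SAP text. On the SAP's own example it is one AE of 6 days against two AEs of 2 and 3 days, a twofold difference in the summarised duration if the gap sentence is followed. Separately, the stated rule puts 6 days on a record with 2 days at Grade 3, a problem that the SAP acknowledges and meets only with a note.

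The reach is narrow: AEIDs, the descriptive duration summary for frequent solicited AEs, and the durations in the Grade 3 listing. Subject-level incidence, maximum grade, time to first onset and actual pausing decisions do not change. The comparison assumes that a Grade 0 day is a gap. The opening text says this directly only for unreported days; for Grade 0 it is inferred. The size in the trial cannot be given, because the frequency of gaps is not in the documents. It should be corrected, but it does not threaten the safety conclusions.

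**What to change.** Reconcile the opening text, the example and the closing notes of SAP Attachment 2 with SAP 7.1.3, so that they share one event definition.

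- **Least disruptive option.** Keep the first-to-last span. Reword the gap sentence so that a gap starts a new record within the same AEID. Label the SAP 7.1.3 duration table *first-to-last span, including symptom-free and unreported days*.
- **Alternative.** Adopt the gap sentence. Correct the AEIDs and the duration in the example, state that Grade 0 and unreported days both count as gaps, and report the longest episode.
- **In either case.** Add the number of consecutive Grade 3 days to the Grade 3 listing. In the example this would show 2.

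The first option costs some SAP wording, a table label and one extra derived variable, with no new data. The alternative also changes how AEIDs and durations are derived. Its drawback is that a single unreported diary day splits an episode and shortens the reported duration, which is the less cautious direction for safety. Choosing between the two is a trade-off for the sponsor; leaving both in the text is what should not stand.
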